11.7.1 Stopping Rules

1. The CCI will be informed monthly by the CRO about the total number of patients who will experience a syncope recurrence (primary endpoint event).
2. When the number of events will reach¹ the predefined limits for interim analyses (40% and 70% of the expected number of events), open queries will be resolved and on site monitoring visits for source data verification will be performed.
3. Unclassified primary endpoint events will be adjudicated (see section 9.9). If available primary endpoint events will be less than the predefined limits for interim analyses after the adjudication process, endpoint point event collection will continue until the required number will be reached.
4. When data set will be cleaned the clinical project manager of the study will inform the appointed independent statistician.
5. The independent statistician will analyze the data according to the Statistical Analysis Plan (SAP). The results will be communicated to the CCI and the sponsor of the study. If the

¹ The number of events may exceed the programmed limit whenever 2 or more events occur at the same time.

primary objective is reached the study stops immediately. The stop date of the study is the date of insertion in the database of the last syncopal recurrence. If the primary objective is not reached the independent statistician will recommend to continue the study until 62 events will be collected. Investigators will not be informed of the results of the interim analyses.

6. After study closure investigators shall complete missing data (apart from the primary events) and close open queries within the following 2 months. Events occurring after the stop date shall not be considered either for primary or for secondary endpoints.

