4.4 Study procedures

At enrolment, patients will receive anonymous syncope and pre-syncope assessment questionnaires to be self-administered upon each primary and secondary endpoint ever experienced and mailed (by ordinary mail) to an external CRO every 3 months after discharge b, using anonymous pre-paid and pre-addressed envelops.

Patients will be also visited in hospital at 12-, and 24-months. More frequent scheduled visits are optional and can be performed according to the site clinical practice. However, any scheduled or unscheduled in-hospital visit must be documented in the appropriate eCRF. Optionally, a 1-month $(\pm 14 \text{ days})$ in-hospital visit may be performed to repeat the TT.

4 Determination of sample size

The study sample size calculation is based on the minimum relative difference in the 2-year incidence of syncopal recurrences as compared with placebo (pacemaker OFF).

The 2-year incidence of the primary endpoint in the control group will be assumed equal to the incidence observed in the control arm of the ISSUE 3 trial: ² this was reported as high as 57%. The ISSUE 3 trial was considered as it selected a large population, had very similar inclusion/exclusion criteria, was recently published.

The BIOSync CLS study is designed to detect a 40% relative reduction of the 2-years incidence of syncopal recurrences (from 57% to 34%) with a statistical Type I and II errors of 0.05 (bilateral) and 0.20, respectively.

Further assumptions:

- Exponential distribution of times to first recurrence
- Accrual time: 2 years
- Total study time: 4 years
- Randomization ratio: 1:1
- Loss incidence: 10% (both arms)

With these assumptions a sample size of 62 patients per study arm (124 in total) is required. This estimate must be further increased by 2%, due to the slight power loss induced by the interim analyses.

In summary, 128 subjects (64 per study arm) are necessary to reach the study primary objective with the required power.

The required number of primary endpoint events is 62, as calculated with the formula:

events =
$$\frac{\left(z_{\alpha/2} + z_{\beta}\right)^{2}}{0.25 \log(HR)}$$

where $z_{\alpha/2}$ and z_{β} are the standard normal percentiles (α =0.05, β =0.20), HR is the expected hazard ratio. A HR of about 0.49 was calculated assuming an exponential model of the survival functions with proportional hazard rates.

5 Database cleaning

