7.1 General methodology

Continuous variables will be summarized using tables of descriptive statistics: number of patients with recorded observations, mean, standard deviation, median, interquartile boundaries, minimum and maximum. Categorical variables will be summarized using counts and percentages. Descriptive statistics will be presented by randomization group.

Comparison of continuous parameters between two groups will be performed using T-test or Wilcoxon Man-Whitney U test, after testing for normality with the Shapiro-Wilk test. Categorical variables will be compared using the Chi-Square or Fisher exact test, as appropriate.

For the analysis of the primary and the secondary endpoint the Kaplan-Meier plots will be generated and the estimated survival functions of the study groups tested with the two- sided log-rank test. Dependence of survival on major baseline predictors will be evaluated with proportional hazard Cox models. Proportionality of hazards will be tested with the Schoenfeld Residuals test. Hazard ratios and relative 95% confidence intervals for each predictor will be calculated, respectively. Data will be censored at the date of last patient contact. The ITT principle will be applied.

All applicable statistical tests will be 2-sided and will be performed using a 5% significance level. All confidence intervals presented will be 95% and two-sided. Statistical calculations will be carried out by using STATA $11.1 \, \text{@}$, SAS $9.3 \, \text{@}$ or R.

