7.6 Interim analysis

Interim analyses will be performed at t=0.4 and 0.7 of the required primary endpoint events or, equivalently, after 25 and 43 endpoint events will be collected. The final analysis will be performed after the study database has been closed out. In order to keep the overall type I error at the level of 0.05, two-sided, symmetric O'Brien-Fleming boundaries generated with the Lan-DeMets spending function approach to group-sequential testing will be assumed as early stopping rules for efficacy.

t	0.40	0.70	1.00
No. endpoint events	25	43	62
Zup	3.3569	2.4445	2.0005
Z_{low}	-3.3569	-2.4445	-2.0005
р	0.0008	0.015	0.05

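### At the final look the ordinary 95% interval does not match the group-sequential boundary, and the plan has no rule for reporting the hazard ratio after an early stop

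*SAP*

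**What the plan says.** SAP 7.6 and Protocol 11.6 plan two efficacy looks, at 25 and 43 of 62 events, with symmetric O'Brien-Fleming "boundaries generated with the Lan-DeMets spending function approach to group-sequential testing". The |Z| limits are 3.3569, 2.4445 and 2.0005; a row labelled p gives 0.0008, 0.015 and 0.05. Protocol 11.7.1 makes the stop binding: if the "primary objective is reached the study stops immediately".

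SAP 7.1 sets one 5% two-sided level for all tests, with no exception for the primary endpoint, and adds: "All confidence intervals presented will be 95% and two-sided". The code in SAP 7.5 runs a log-rank test and then a Cox model on randomization group with the default interval.

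Neither document names an estimate, interval or p-value adjusted for the looks, says that 7.6 takes precedence over 7.1, or comments on reading the HR after an early stop.

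**The concern.** The looks are allowed for in the test but not in the estimate. This matters in two places.

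- **Final look.** A statistician who follows 7.1 compares p with 0.05 and reads a 1.96-based interval. One who follows 7.6 compares |Z| with 2.0005. In a narrow band they reach opposite conclusions from the same data, and the tabled p of 0.05 favours the wrong reading.
- **Early stop.** A trial stops at a look only if the observed effect is large, so the HR reported from such a stop is selected for being extreme. This would not be rare: at the design HR about 57% of successful trials are early stops.

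At stake are the published HR and interval, and the choice of estimator, which would otherwise be made after the result is known.

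**Working it through.** **Inputs.** From the SAP's sample-size section: errors "with a statistical Type I and II errors of 0.05 (bilateral) and 0.20, respectively", "Randomization ratio: 1:1", and 2-year incidences of 57% and 34%. Looks and boundaries are from SAP 7.6. Z is positive when CLS does better. The information for log HR is taken as events/4, so SE = 2/√events: 0.400, 0.305 and 0.254 at the three looks.

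**Reproducing the plan's figures.**
- HR = ln(0.66)/ln(0.43) = 0.492, in line with the stated value of about 0.49.
- Events = (1.960 + 0.842)² / (0.25 × [ln 0.49]²) = 61.7, rounded up to 62. The printed formula lacks the square on log(HR) and would give about −44; this is a misprint, and 62 comes from the squared form.
- O'Brien-Fleming-type spending of 0.025 per side at 0.4, 0.7 and 1.0 gives 3.3569, 2.4445 and 2.0005 exactly. Simulated overall two-sided type I error is 0.050.
- HR needed to cross = exp(−Z × SE): 0.26, 0.47 and 0.60.

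**The p row.** Nominal p = 2[1 − Φ(Z)] is 0.0008, 0.0145 and 0.0454. Cumulative two-sided alpha spent, 4[1 − Φ(2.2414/√t)], is 0.0008, 0.0148 and 0.0500. The tabled 0.05 is therefore the cumulative alpha, not the p-value at Z = 2.0005.

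**Final look: ordinary against stage-wise interval.** Ordinary: exp(−Z × 0.254 ± 1.96 × 0.254). Stage-wise: solve for the log HR at which the probability of an outcome at least as extreme, with an earlier crossing ranked as more extreme, is 0.025 in each tail (0.5 for the median-unbiased estimate).

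| Z | Ordinary HR (95% CI) | Stage-wise HR (95% CI) |
|---|---|---|
| 2.0005 | 0.602 (0.366–0.990) | 0.605 (0.367–1.000) |
| 2.5 | 0.530 (0.322–0.872) | 0.543 (0.327–0.913) |

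The probability of ending at the final look with |Z| between 1.96 and 2.0005 is 0.4% at HR 1, 1.1% at 0.49 and 1.5% at 0.60. Applying the 5% rule there would raise type I error to about 0.050 + 0.004 = 0.054.

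**Interim looks: the same comparison.**

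| Look, Z | Ordinary | Stage-wise | Repeated CI |
|---|---|---|---|
| 1, 3.3569 | 0.261 (0.119–0.572) | 0.261 (0.119–0.572) | 0.068–1.00 |
| 2, 2.4445 | 0.474 (0.261–0.863) | 0.475 (0.261–0.864) | 0.225–1.00 |

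The repeated CI uses the look's own boundary in place of 1.96: exp(−Z × SE ± boundary × SE).

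**Behaviour over repeated trials** (2,000,000 simulated score paths; geometric mean HR; coverage of the ordinary 95% CI), at the design HR of 0.492:

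| Outcome | Probability | Mean HR | Coverage |
|---|---|---|---|
| Stop at look 1 | 5.7% | 0.22 | 56% |
| Stop at look 2 | 39.7% | 0.39 | 97.5% |
| Any early stop | 45.3% | 0.36 | 92% |
| Final look | 54.7% | 0.57 | 95.5% |
| All trials | 100% | 0.465 | 94.1% |

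At an assumed true HR of 0.70, 10.2% stop early, with mean HR 0.40 and coverage 73%; over all trials the figures are 0.686 and 94.4%. Given an early stop, the repeated CI covers 99.6% at the design HR and 94.5% at 0.70.

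**The case against.** The best defence is that success rests on the log-rank statistic and the boundaries, which reproduce exactly; no text makes the Cox interval a decision criterion, so an ordinary HR beside a protected test is a reporting choice. That stands as far as type I error goes: nothing here shows the planned boundaries to be invalid. It does not settle the final look, because 7.1 also sets the test level at 5% without exception and the table shows 0.05 there.

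A reader might infer more than the documents support:

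- *That the interval is wrong whenever the trial stops at a look.* It is not. The stage-wise interval equals the ordinary one at look 1 and differs only in the third decimal at the look-2 boundary. Coverage at look 2, where most early stops fall, is 97.5% at the design HR. The 56% at look 1 belongs to a stop with under 6% probability.
- *That the published HR will overstate the benefit.* That is an average over trials that stop early. Trials reaching the final look lean the other way (0.57), and over all trials the shift is from 0.49 to 0.465.
- *That a stage-wise analysis would cure the early-stop exaggeration.* It would not: at look 1 the estimate is unchanged, and at look 2 it hardly moves. The repeated CI keeps coverage, at the price of a much wider interval, but does not move the point estimate.

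**Conclusion.** The point holds as a mismatch in reporting and precedence, not as a failure of the test. At the final look the 5% level and the ordinary 95% interval contradict the 2.0005 boundary in about 1.1% of trials at HR 0.49 and 1.5% at 0.60. The interval is also somewhat too favourable beyond that band (upper limit 0.872 against 0.913 at Z = 2.5). After an early stop the ordinary HR is exaggerated on average (0.36 against 0.49, with about a 45% chance of such a stop at the design HR), and the plan gives no warning of it. Overall bias and loss of coverage are small.

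The figures assume a normal score approximation, looks at exactly 25, 43 and 62 events, and proportional hazards. Protocol 11.7.1 allows the counts to overshoot slightly. HRs other than 0.49 are assumptions shown as a range. The conflict between 7.1 and 7.6 can be seen without any simulation.

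**What to change.** In SAP 7.5 and 7.6:

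1. State that the 7.6 boundaries override the 5% rule of 7.1 for the primary endpoint.
2. Give the final nominal p as 0.0454. If the existing row is kept, label it cumulative alpha.
3. Pre-specify one interval for the primary HR that is consistent with the boundaries: either a stage-wise CI with the median-unbiased HR, or a repeated CI. They are not interchangeable. The stage-wise CI is close to the ordinary one at an interim stop. The repeated CI is clearly wider there, but its coverage given an early stop stays near or above 95% for a true HR of 0.49 to 0.70.
4. Show the ordinary Cox HR and CI beside it, labelled as unadjusted for the looks.
5. Add a sentence that an HR from an early stop overstates the effect on average.

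The cost is one SAP paragraph and standard group-sequential software output. Design, sample size and conduct do not change. The downside is a slightly less favourable final-look interval, or a wider interval if the repeated CI is chosen, and two sets of figures to explain.

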7.2 Handling of missing data

Missing or spurious data is not substituted; all data – as far as correctly measured – is analyzed. No method of imputation will be used for missing data.

In some cases, particular clinical data is excluded from analysis. The following reasons are possible:

FOR-137- 059-B / SOP-137-060.020 / CRQ-15-00950

- Data is not measured as described in the latest applicable version of the clinical investigation plan.
- Data is evaluated beyond the required follow-up schedule.
- Patient has to be excluded because she/he does not fulfill the exclusion/inclusion criteria.
- Patient requires that all recorded data has to be deleted.
- There is evidence of incomplete or incorrect patient consent process.

Baseline list variables 7.3

The following table reports the description of relevant baseline variables.

Variable name	List of values	Unit of measure	Description	
rd_display	0 (ODO); 1 (DDD-CLS)	-	Randomization group	
gi_age	Numeric	Years	Age at enrolment	
gi_gender	0 (Male); 1 (Female)	(A)	Gender	
hs_syncop_life	Numeric	Unit	Total number of syncope during lifetime	
hs_syncop_lastyear	Numeric	Unit	Total number of syncope during last year	
hs_age_syncop	Numeric	Years	Age of first syncope	
hs_histor_presync	0 (No); 1 (Yes)		History of pre-syncope	
prevepi_hosp_sync	0 (No); 1 (Yes)	3=	Was the patient hospitaliz ed because of syncope?	
com_hypertension	0 (No); 1 (Yes)	S -	Hypertension	
com diabetes	0 (No); 1 (Yes)	ide:	Diabetes	
com_neuro_disease	0 (No); 1 (Yes)	ya:	Neurological disease	
hdis_hypertensive_disease	0 (No); 1 (Yes)	¥	Hypertensive disease	
hdis_ca_disease	0 (No); 1 (Yes)	0 5	Coronary artery disease	
hdis_valvular_disease	0 (No); 1 (Yes)	: +:	Valvular disease	
hdis_hyp_cardiomyopath	0 (No); 1 (Yes)	:=	Hypertrophic cardiomyopathy	
hdis_dilated_cardiomyopath	0 (No); 1 (Yes)	-	Dilated cardiomyopathy	
arr fst av block	0 (No); 1 (Yes)	-	First degree AV block	
arr atr tachycardia	0 (No); 1 (Yes)	De:	Atrial tachycardia	
arr_paroxy_afib_af	0 (No); 1 (Yes)	-	Paroxysmal atrial fibrillation/flutter	
arr_perm_afib_af	0 (No); 1 (Yes)	-	Permanent atrial fibrillation/flutter	
ecg_normal_sr	0 (No); 1 (Yes)	=	Normal sinus rhythm at enrolment	
ecg_afib_af	0 (No); 1 (Yes)	#	Atrial fibrillation/Flutter at enrolment	
ecg_mean_hr	Numeric	Beats per minute	Mean heart rate	
ecg_qrs	Numeric	msec	QRS duration	
ecg_pr_interval	Numeric	msec	PR interval	
echo_ejection_fraction	Numeric	%	Ejection fraction	
ortho_supl_syst_bp	Numeric	mmHg	Supine systolic blood pressure	
ortho_low_syst_bp	Numeric	mmHg	Lowest upright systolic blood pressure	
ortho_max_syst_bp	Numeric	mmHg	Maximal drop in systolic blood pressure	
carotid_rr_pause	Numeric	sec	Longest RR pause at carotid sinus massagge	
carotid_syncope_presyncope	0 (No); 1 (Yes)	=	Syncope or pre-syncope at carotid	

			sinus massagge	
cm_ace	0 (No); 1 (Yes)	(E	ACE Inhibitors	
cm_anticoagulant	0 (No); 1 (Yes)	.: 	Anticoagulants	
cm_antiplatelets	0 (No); 1 (Yes)	9 81	Antiplatelets	
cm_b_blocker	0 (No); 1 (Yes)	15 2 1	Beta-blockers	
tt_response	0 (Pre-syncope); 1 (Syncope)		Response to tilt test	
tt_pause_max	Numeric	sec	Maximum asystolic pause at tilt test	
tt_pause_type	0 (Sinus arrest); 1 (AV block)	*	Type of pause at tilt test	
tt_time_pre_sync	Numeric	min	Time to symptom onset (from tilt up if positive during passive phase or from TNT administration if positive during the TNT phase)	
tt_bp_pre_sync	Numeric	mmHg	Systolic BP at symptom onset	
tt_low_bp	Numeric	mmHg	Lowest systolic blood pressure during tilt test	

7.4 Baseline data analysis

*Baseline Analysis (STATA script)

*Age at enrolment tabstat gi_age, statistics(mean sd p50 p75 p25) by(rd_display) columns (statistics) swilk gi_age ranksum gi_age, by(rd_display)

*Gender tabulate gi_gender rd_display, chi2 column exact

*Total number of syncope during lifetime tabstat hs_syncop_life, statistics(mean sd p50 p75 p25) by(rd_display) columns (statistics) swilk hs_syncop_life ranksum hs_syncop_life, by(rd_display)

*Total number of syncope during last year tabstat hs_syncop_lastyear, statistics(mean sd p50 p75 p25) by(rd_display) columns (statistics) swilk hs_syncop_lastyear ranksum hs_syncop_lastyear, by(rd_display)

*Age of first syncope tabstat hs_age_syncop, statistics(mean sd p50 p75 p25) by(rd_display) columns (statistics) swilk hs_age_syncop ranksum hs_age_syncop, by(rd_display)

*History of pre-syncope tabulate hs_histor_presync rd_display, chi2 column exact

*Was the patient hospitaliz ed because of syncope? tabulate prevepi_hosp_sync rd_display, chi2 column exact

*Hypertension tabulate com_hypertension rd_display, chi2 column exact

*Diabetes tabulate com_diabetes rd_display, chi2 column exact

*Neurological disease

tabulate com_neuro_disease rd_display, chi2 column exact

*Hypertensive disease tabulate hdis_hypertensive_disease rd_display, chi2 column exact

*Coronary artery disease tabulate hdis_ca_disease rd_display, chi2 column exact

*Valvular disease tabulate hdis_valvular_disease rd_display, chi2 column exact

*Hypertrophic cardiomyopathy tabulate hdis_hyp_cardiomyopath rd_display, chi2 column exact

*Dilated cardiomyopathy tabulate hdis_dilated_cardiomyopath rd_display, chi2 column exact

*First degree AV block tabulate arr_fst_av_block rd_display, chi2 column exact

*Atrial tachycardia tabulate arr_atr_tachycardia rd_display, chi2 column exact

*Paroxysmal atrial fibrillation/flutter tabulate arr_paroxy_afib_af rd_display, chi2 column exact

*Permanent atrial fibrillation/flutter tabulate arr_perm_afib_af rd_display, chi2 column exact

*Normal sinus rhythm at enrolment tabulate ecg_normal_sr rd_display, chi2 column exact

*Atrial fibrillation/Flutter at enrolment tabulate ecg_afib_af rd_display, chi2 column exact

*Mean heart rate tabstat ecg_mean_hr, statistics(mean sd p50 p75 p25) by(rd_display) columns (statistics) swilk ecg_mean_hr ranksum ecg_mean_hr, by(rd_display)

*QRS duration tabstat ecg_qrs, statistics(mean sd p50 p75 p25) by(rd_display) columns (statistics) swilk ecg_qrs ranksum ecg_qrs, by(rd_display)

*PR interval tabstat ecg_pr_interval, statistics(mean sd p50 p75 p25) by(rd_display) columns (statistics) swilk ecg_pr_interval ranksum ecg_pr_interval, by(rd_display)

*Ejection fraction tabstat echo_ejection_fraction, statistics(mean sd p50 p75 p25) by(rd_display) columns (statistics) swilk echo_ejection_fraction ranksum echo_ejection_fraction, by(rd_display)

*Supine systolic blood pressure tabstat ortho_supl_syst_bp, statistics(mean sd p50 p75 p25) by(rd_display) columns (statistics) swilk ortho_supl_syst_bp ranksum ortho_supl_syst_bp, by(rd_display)

*Lowest upright systolic blood pressure tabstat ortho_low_syst_bp, statistics(mean sd p50 p75 p25) by(rd_display) columns (statistics)

swilk ortho_low_syst_bp
ranksum ortho_low_syst_bp, by(rd_display)

*Maximal drop in systolic blood pressure tabstat ortho_max_syst_bp, statistics(mean sd p50 p75 p25) by(rd_display) columns (statistics) swilk ortho_max_syst_bp ranksum ortho_max_syst_bp, by(rd_display)

*Longest RR pause at carotid sinus massagge tabstat carotid_rr_pause, statistics(mean sd p50 p75 p25) by(rd_display) columns (statistics) swilk carotid_rr_pause ranksum carotid_rr_pause, by(rd_display)

*Syncope or pre-syncope at carotid sinus massagge tabulate carotid_syncope_presyncope rd_display, chi2 column exact

*ACE Inhibitors tabulate cm_ace rd_display, chi2 column exact

*Anticoagulants tabulate cm_anticoagulant rd_display, chi2 column exact

*Antiplatelets tabulate cm_antiplatelets rd_display, chi2 column exact

*Beta-blockers tabulate cm_b_blocker rd_display, chi2 column exact

*Response to tilt test tabulate tt_response rd_display, chi2 column exact

[figure not shown]
*Maximum asystolic pause at tilt test tabstat tt_pause_max, statistics(mean sd p50 p75 p25) by(rd_display) columns (statistics) swilk tt_pause_max ranksum tt_pause_max, by(rd_display)

*Type of pause at tilt test tabulate tt_pause_type rd_display, chi2 column exact

*Time to symptom onset(from tilt up if positive during passive
*phase or from TNT administration if positive during the TNT phase)
tabstat tt_time_pre_sync, statistics(mean sd p50 p75 p25) by(rd_display) columns (statistics)
swilk tt_time_pre_sync
ranksum tt_time_pre_sync, by(rd_display)

*Systolic BP at symptom onset tabstat tt_bp_pre_sync, statistics(mean sd p50 p75 p25) by(rd_display) columns (statistics) swilk tt_bp_pre_sync ranksum tt_bp_pre_sync, by(rd_display)

[figure not shown]
*Lowest systolic blood pressure during tilt test tabstat tt_low_bp, statistics(mean sd p50 p75 p25) by(rd_display) columns (statistics) swilk tt_low_bp ranksum tt_low_bp, by(rd_display)

7.5 Evaluation of study objectives

The BIOSync CLS study (BA103, CIP ver. 7.0) gathers primary and secondary endpoints' data through self-administered patient questionnaires. In order to ensure double-blinding in endpoint assessment, the questionnaires will be collected by external personnel of an appointed CRO. This process is descripted in detail in the Charter for patient questionnaire collection and adjudication, version 2.0, 06-Mar-2017, and summarized in the below image.

At the end of the adjudication the following derived variables will be created.

Variable name	List of values	Unit of measure	Description	
pe	0 (No); 1 (Yes)	*	Occurrence of syncope episode	
time_pe	Numeric	days	If pe=1: time to the first post	
			randomization recurrence of a	
			syncopal episode;	
			If pe=0: total follow-up time	
se	0 (No); 1 (Yes)	-	Occurrence of pre-syncope or	
			syncope episode	
time_pe	Numeric	days	If pe=1: time to the first post	
			randomization recurrence of a pre-	
			syncope or syncope episode	
			whichever comes first.;	
			If pe=0: total follow-up time	

The analysis of the primary and secondary study objectives will be performed with the following code (STATA language).

stset time_pe, failure(pe==1)

*Kaplan_meier plots generation

sts graph by(rd_display), ci risktable

*Comparison of survivors functions

sts test rd_display, logrank

*Proportional hazard Cox models for major baseline predictors

stcox rd display

estat phtest

stcox gi_age

stcox gi_gender

stcox hs syncop life

stcox hs_syncop_lastyear

stcox ecg_mean_hr

stcox tt_response

stcox tt_pause_max

stcox tt_pause_type

stcox tt_time_pre_sync

^{*}Study objectives evaluation

^{*}Primary endpoint

*Secondary endpoint

stset time_se, failure(se==1)

*Kaplan_meier plots generation
sts graph, by(rd_display) ci

*Comparison of survivors functions
sts test rd_display, logrank

*Proportional hazard Cox models for major baseline predictors
stcox rd_display
estat phtest
stcox gi_age
stcox gi_gender

stcox hs_syncop_lastyear stcox ecg_mean_hr

stcox tt_response stcox tt_pause_max

stcox hs_syncop_life

stcox tt_pause_type stcox tt_time_pre_sync

stcox tt_low_bp

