11 STATISTICAL CONSIDERATIONS

11.1 Statistical design, method and analytical procedures

Standard summary statistics will be calculated for all patients and study outcome variables. Categorical data will be summarized via distributions of absolute and relative frequencies. For all relevant parameters 95% confidence intervals will be calculated.

For the analysis of the primary endpoint and the secondary endpoint the Kaplan-Meier plots will be generated and the estimated survival functions of the study groups tested with the two-sided log-rank test. Dependence of survival on major baseline predictors will be studied with proportional hazard Cox models. Hazard ratios and relative 95% confidence intervals for each predictor will be calculated, respectively. Data will be censored at the date of last patient contact. The ITT principle will be applied.

Statistical calculations will be carried out by using STATA 11.1 ®, SAS 9.3 © or R.

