11.2 Sample size calculation

The study sample size calculation is based on the minimum relative difference in the 2-year incidence of syncopal recurrences as compared with placebo (pacemaker OFF).

The 2-year incidence of the primary endpoint in the control group will be assumed equal to the incidence observed in the control arm of the ISSUE 3 trial:⁽¹⁶⁾ this was reported as high as 57%. The ISSUE 3 trial was considered as it selected a large population, had very similar inclusion/exclusion criteria, was recently published.

The BIOSync CLS study is designed to detect a 40% relative reduction of the 2-years incidence of syncopal recurrences (from 57% to 34%) with a statistical Type I and II errors of 0.05 (bilateral) and 0.20, respectively.

Further assumptions:

- Exponential distribution of times to first recurrence
- Accrual time: 2 years
- Total study time: 4 years
- Randomization ratio: 1:1
- Loss incidence: 10% (both arms)

With these assumptions a sample size of 62 patients per study arm (124 in total) is required. This estimate must be further increased by 2%, due to the slight power loss induced by the interim analyses (see section 11.6).

In summary, 128 subjects (64 per study arm) are necessary to reach the study primary objective with the required power.

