11.2.1 Required number of primary endpoint events

The required number of primary endpoint events is 62, as calculated with the formula:

$$events = \frac{(z_{\alpha/2} + z_{\beta})^2}{0.25 \log(HR)}$$

where $z_{\alpha/2}$ and z_{β} are the standard normal percentiles ($\alpha=0.05$, $\beta=0.20$), HR is the expected hazard ratio. A HR of about 0.49 was calculated assuming an exponential model of the survival functions with proportional hazard rates.

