11.3 Level of significance and the power of the study

Target study power: 80%

Significance level: 0.05 (bilateral)

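### A cheap improvement, not an error: no pre-specified model contains both the randomised arm and a baseline predictor, so the treatment effect is never adjusted for syncope burden or age

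*SAP*

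**What the plan says.** SAP 7.1 and protocol 11.1 both name the two-sided log-rank test for the primary and secondary endpoints and describe the Cox models in almost the same words. The SAP has "Dependence of survival on major baseline predictors will be evaluated with proportional hazard Cox models"; the protocol has "Dependence of survival on major baseline predictors will be studied with proportional hazard Cox models". Neither names a covariate-adjusted treatment model or a stratified log-rank test.

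The code in SAP 7.5 follows that wording. For each endpoint it runs the log-rank test by arm, then `stcox rd_display` with a proportional-hazards check. One-variable models follow for age, gender, lifetime and last-year syncope counts, mean heart rate and tilt-test variables. The line for last-year burden is "stcox hs_syncop_lastyear". No command holds both the arm and a predictor.

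Age and both syncope counts are listed as baseline variables in SAP 7.3. Protocol 8.3.1 states that randomisation is not stratified.

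The sizing is for the unadjusted comparison. Protocol 11.2 sets the target as "from 57% to 34%) with a statistical Type I and II errors of 0.05 (bilateral) and 0.20, respectively", and protocol 11.2.1 gives "A HR of about 0.49 was calculated assuming an exponential model of the survival functions with proportional hazard rates" and "The required number of primary endpoint events is 62". The sample-size section of the SAP concludes that "128 subjects (64 per study arm) are necessary to reach the study primary objective with the required power".

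**The concern.** The sponsor groups these variables as major baseline predictors, yet uses none of them in the comparison of arms. If syncope burden predicts recurrence, a proportional hazards comparison that leaves it out has less power than one that includes it. Burden is balanced neither by stratified randomisation nor by the analysis. The predictor models, lacking the arm, also pool two groups whose recurrence rates are expected to differ.

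There is a second practical gap. SAP 7.4 runs between-arm tests on 40 baseline variables. At the 5% level about 40 × 0.05 = 2 would be significant by chance (treating the tests as independent), and the SAP does not say what follows from that. Without a pre-specified adjusted model, any adjustment would be chosen after the imbalances are seen.

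At stake are some efficiency and a clean answer to the question of adjustment. The validity of the primary test is not at stake.

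**Working it through.** **1. The plan's own figure.** Inputs from protocol 11.2 and 11.2.1: 2-year incidence 57% and 34%, two-sided α = 0.05, β = 0.20.

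- HR = ln(1 − 0.34) / ln(1 − 0.57) = ln 0.66 / ln 0.43 = 0.492, matching the stated 0.49.
- Events = (1.960 + 0.842)² / [0.25 × (ln HR)²] = 7.849 / (0.25 × 0.502) = 62.5. At HR = 0.49 exactly it is 61.7, so 62. (The printed formula omits the square on log(HR); 62 is reached only with it.)

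This is an unadjusted calculation, so the planned 80% does not rely on covariate adjustment.

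**2. Effect of adjustment, by simulation.** Inputs:

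- 64 patients per arm.
- Hazard = λ(arm) × exp(s × Z), where Z is a standard normal covariate. The λ values are solved so that the marginal 2-year incidence stays at 57% and 34%.
- Loss of 10% over 2 years: exponential rate −ln(0.9)/2 = 0.053 per year.
- Follow-up capped at 24 months (protocol 8.8.6), giving about 56 events.
- One final test at |Z| > 2.0005, the last boundary in protocol 11.6; interim looks are not simulated.
- s, the log hazard ratio per SD, is **assumed**; no document gives it.

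Simulation A (3,000 trials per row; Monte Carlo standard error √(0.75 × 0.25 / 3000) ≈ 0.8 points) compares the log-rank test with the arm term of a Cox model holding arm and the covariate. Simulation B adds a second covariate with no prognostic value, which is closer to a two-covariate model in practice.

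| s (HR per SD) | A: log-rank | A: adjusted | B: log-rank | B: adjusted |
|---|---|---|---|---|
| 0 (1.00) | 74.7% | 73.5% | 74% | 74% |
| 0.3 (1.35) | 73.7% | 75.2% | 72% | 74% |
| 0.5 (1.65) | 74.3% | 79.3% | 73% | 77% |
| 0.7 (2.0) | 75.0% | 84.6% | 74% | 84% |

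The differences are −1.2 and 0 points at s = 0, +1.5 and +2 at 0.3, +5.0 and +4 at 0.5, and +9.6 and +10 at 0.7. Type I error was 4.5–5.0% in A, for both tests, and 4.4–5.4% in B.

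With the 2 to 4 years of follow-up that the sample-size calculation assumes, A gives 80.6% vs 80.4%, 81.7% vs 83.8%, 80.9% vs 85.5% and 78.6% vs 90.2% for the same four strengths. The pattern does not depend on the cap.

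**3. What the adjusted hazard ratio estimates.** At s = 0.5 under the cap, the average fitted hazard ratio was 0.48 without and 0.46 with the covariate. The adjusted value is conditional on the covariate and is a different quantity.

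**The case against.** The strongest reply is that nothing here is wrong. The log-rank test is the declared primary test, the 62 events are derived for it, and randomisation protects its level; chance imbalance is already within its type I error. The Cox models have a different stated purpose, which is to describe predictors. All of this stands.

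A reader might infer that power is simply being given away. The documents do not support that. They give no prognostic strength for any covariate. Calling the list major predictors does not single out or quantify last-year syncope count, and the entry criterion of at least two syncopes in the last year (protocol 8.8.2) removes the low end of its range. At s = 0 there is nothing to gain.

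A reader might also take the 74–75% in the table as a shortfall caused by the missing adjustment. It is not: it comes from the 24-month cap, which yields about 56 events rather than 62. Nor is the lower adjusted hazard ratio evidence of bias in the unadjusted one. Part of that gap is non-collapsibility, and the hypotheses in protocol 7.2.1 and SAP 3.2 are stated for marginal 2-year survival.

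Two practical objections also stand.

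- SAP 7.2 rules out imputation, so an adjusted model would drop anyone with a missing covariate, contrary to intention to treat. Protocol 9.2 does not name syncope counts among its baseline items, although SAP 7.3 does. In a separate simulation of 4,000 trials with an assumed 5% missing at random and s = 0.3, adjusted power was 72.0%, below the log-rank's 73.7%.
- Under protocol 13, a change that affects data analysis is substantial and needs ethics committee approval, so changing the primary test is more than a code edit.

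These objections limit the claim and shape the remedy. They do not remove the case for fixing an adjusted model in advance.

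**Conclusion.** The point holds as an inexpensive improvement. The SAP specifies no adjusted treatment effect, although suitable baseline values are in its own dataset and randomisation is unstratified. Under the 24-month cap, adjustment changes power by about 0 points if the covariate is not prognostic, 1–2 points at an assumed log hazard ratio per SD of 0.3, 4–5 at 0.5 and about 10 at 0.7.

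These figures rest on the assumed strength, a correctly specified and complete covariate, and a single final look. The planned analysis remains valid and consistent with its sizing. The pass/fail decision gains power only if the adjusted test is made primary.

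**What to change.** Before any unblinded look, replace the lists of one-variable models with one pre-specified Cox model per endpoint containing `rd_display`, log(`hs_syncop_lastyear`) and `gi_age`. Add a simple rule, as a stated exception to SAP 7.2, that keeps patients with a missing covariate in the intention-to-treat analysis; for example, substitute the mean pooled over both arms. The rule should also cover a recorded count of zero, for which the log is undefined.

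Then choose one of two routes for the primary endpoint:

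- **Adjusted test as primary.** The arm term becomes the primary test by protocol amendment, with the log-rank as sensitivity analysis. Only this route can raise pass/fail power.
- **Log-rank kept for the sequential decision.** The adjusted hazard ratio is reported beside the unadjusted one as the pre-specified conditional estimate. This adds no pass/fail power but settles the adjustment in advance.

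**Cost.** No new patients or visits, and no data beyond what SAP 7.3 already lists. The second route is a SAP text and code change; the first needs a substantial amendment with ethics approval. Timing matters, because protocol 11.7.1 sends interim results to the coordinating investigator and the sponsor. The estimand must be stated, since the adjusted hazard ratio is conditional rather than marginal. On the first route, the 25-event look would have only 25 / 3 ≈ 8 events per parameter, and the model's behaviour there should be checked before it is adopted.
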